# 8.3.5 SERIOUS ADVERSE EVENT REPORTING

Related, unexpected SAE's resulting in death or any life-threatening outcome will be reported to IRBMED and the DSMB within 7 calendar days of becoming aware of the event. Other related, unexpected SAE's will be reported to IRB-MED and the DSMB within 14 days of becoming aware of the event.

Unrelated, unexpected SAE's will be reported per standard IRBMED guidelines and in conjunction with regularly scheduled DSMB meetings.

Note, there are no related, expected SAE's associated with this study.

## 8.3.6 REPORTING EVENTS TO PARTICIPANTS

If the study team becomes aware of new knowledge regarding related, unexpected AE's/SAE's that may affect other current or future study participants, the study team will seek input from the DSMB as to whether/how to communicate this information to other current participants and/or whether/how to amend the IRB-MED approved informed consent documents for future participants. Re-consenting will be performed for subjects actively involved in the study if deemed necessary by the PI, IRMBED, or DSMB.

## 8.3.7 EVENTS OF SPECIAL INTEREST

N/A

#### 8.3.8 REPORTING OF PREGNANCY

If a study participant becomes pregnant during the study period, or becomes aware of a previously unidentified pre-existing pregnancy during the study period, they will be permitted to continue study participation at the discretion of their treating obstetrician (or other physician responsible for managing their pregnancy, e.g., family medicine physician) and a letter of clearance for ongoing study participation will be requested to document this clearance.

## 8.4 UNANTICIPATED PROBLEMS

## 8.4.1 DEFINITION OF UNANTICIPATED PROBLEMS (UP)

The Office for Human Research Protections (OHRP) considers unanticipated problems involving risks to participants or others to include, in general, any incident, experience, or outcome that meets all of the following criteria:

- Unexpected in terms of nature, severity, or frequency given (a) the research procedures that are described in the protocol-related documents, such as the Institutional Review Board (IRB)approved research protocol and informed consent document; and (b) the characteristics of the participant population being studied;
- Related or possibly related to participation in the research ("possibly related" means there is a reasonable possibility that the incident, experience, or outcome may have been caused by the procedures involved in the research); and
- Suggests that the research places participants or others at a greater risk of harm (including physical, psychological, economic, or social harm) than was previously known or recognized.

## 8.4.2 UNANTICIPATED PROBLEM REPORTING

The study team will report unanticipated problems (UPs) to IRBMED. The UP report will include the following information:

- Protocol identifying information: protocol title and number, PI's name, and the IRB project number;
- A detailed description of the event, incident, experience, or outcome;
- An explanation of the basis for determining that the event, incident, experience, or outcome represents an UP;
- A description of any changes to the protocol or other corrective actions that have been taken or are proposed in response to the UP.

To satisfy the requirement for prompt reporting, UPs will be reported using the following timeline:

- UPs that are actual AEs or SAEs will be reported to IRB-MED as described above in Section 8.3.5-8.3.6.
- Any other UPs representing newly identified possibility of previously unsuspected harm will be reported to IRB-MED within 14 days of the study team becoming aware of the problem.
- If IRB-MED concurs that a UP exists, the UP will be reported to appropriate institutional and external officials as required under IRB-MED's reporting policies and procedures.

## 8.4.3 REPORTING UNANTICIPATED PROBLEMS TO PARTICIPANTS

If UPs are identified that may affect current or future study participants, the study team will seek input from the DSMB as to whether/how to communicate this information to current participants and/or whether/how to amend the IRBMED approved informed consent documents for future participants.

## 9 STATISTICAL CONSIDERATIONS

#### 9.1 STATISTICAL HYPOTHESES

#### **Primary Efficacy Endpoint:**

There will be evidence of a dose-response effect for neck strengthening exercise on net head acceleration under direct load application proportional to the volume load of exercise.

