# Funded by: NIH: Eunice Kennedy Shriver National Institute of Child Health and Human Development

Version Number: v.2.3

15 May 2023

Summary of Changes from Previous Version:

Affected Section(s)	Summary of Revisions Made	Rationale
1.2, 2.3.2, 4.1, 4.2, 4.3, 6.1.1, 6.1.2, 6.2, 9.2, 9.4.5	Low-Volume exercise group removed from protocol.	Reduce enrollment following COVID pandemic.
1.3	Clarification to criteria defining protocol deviation - updating number of days that create a deviation.	Reducing documentation burden associated with schedule deviations
2.3.1, 2.3.3, 5.2	Removal or MRI contraindication as exclusion criteria.	Low enrollment number. MRI data is not used for primary outcome. Removing this criterion may increase the number of eligible participants.

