## 4.3 JUSTIFICATION FOR DOSE

All subjects will exercise 2 days per week under the direct supervision of a study-assigned strength coach (National Strength and Conditioning Association Certified Strength and Conditioning Specialist, CSCS, certification), with a minimum of 1 day of rest between exercise sessions. Subjects will be assigned either to a high intensity neck strengthening exercise group or to a control exercise group performing only "shoulders-down" resistance exercises not directly targeting the neck. All exercises will be performed in accordance with National Strength and Conditioning Association standards. The neck strengthening program will include manual resistance exercises in sagittal-plane flexion and extension, coronal-plane lateral flexion to the left and right, and axial-plane rotation to the left and right, as well as dumbbell shoulder shrugs as previously described by our group. For each group, the exercise program

will progress in volume and intensity over the duration of the study, to accommodate muscular fitness adaptation. Such progression is considered vital to the long-term efficacy of resistance exercise programming.

The volume load of neck strengthening exercise will be calculated using a modified protocol previously employed by our group for the elbow flexors. For shoulder shrugs the volume load for each exercise session will be defined as the product of the dumbbell weight x the force of gravity (g= 9.8 m/s2) x the number of repetitions performed during the exercise session, to yield a volume load for the exercise session in N. During manual resistance exercise, the strength coach will hold a hand-held dynamometer against the subject's head to measure and record the force applied during manual resistance. For both dumbbell shrugs and manual resistance exercises, the total cumulative exercise volume load will be defined as the sum of the individual session volume loads over all exercise sessions completed by the subject. Since subjects assigned to the control group will not perform neck strengthening exercise, their exercise volume load will remain zero throughout the study.

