#### 6.2 MEASURES TO MINIMIZE BIAS: RANDOMIZATION AND BLINDING

Subjects will be randomized using a centralized electronic randomization tool with equal allocation to the control and high-intensity neck strengthening groups. Balanced block randomization will be used to ensure equal sex and age category balance between the groups. Age category will correspond to high school under-class (i.e., age 13.0 - 16.49 years at the time of randomization) vs. upper-class (i.e., age 16.50 – 19.99 years) status given the typical maturation occurring in adolescents through the high school years. Subjects will be considered enrolled in the trial upon randomization and available data will be included in the intention to treat analysis. The Study Statistician, Strength Coach, Study Coordinator, and PI (or his Co-I designee when necessary to make a determination of AE relatedness to the study) will not be blinded to subject group allocation. Other members of the study team, including those responsible for performing the laboratory- and radiology-based assessment will be blinded to group allocation status. Subjects will not be informed of their group allocation status, although they will be aware of whether or not they are performing neck strengthening exercises during their exercise sessions. Subjects will be instructed not to discuss whether they are performing neck strengthening exercises during their exercise sessions.

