## 6.3 STUDY INTERVENTION COMPLIANCE

Subjects will be given the opportunity to make-up any missed exercise sessions within 7 days of the originally scheduled date, so long as at least one day of rest is scheduled between successive exercise sessions. Subjects will be considered to have successfully completed the exercise protocol if at least 20 of the 24 exercise sessions are attended, with no more than 2 missed sessions during any 4-week block.

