#### **Secondary Efficacy Endpoint:**

There will be evidence of a dose-response effect for neck strengthening exercise on net head acceleration under indirect load application proportional to the volume load of exercise.

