## 9.4.2 ANALYSIS OF THE PRIMARY AND SECONDARY EFFICACY ENDPOINTS

We expect a percentage reduction in net head acceleration as the volume load of exercise performed increases over the 12 week exercise program, so we will assess net head acceleration on a logarithmic scale to allow us to model and detect a constant change. For example, a 20% reduction in net head acceleration corresponds to a difference of log(.8) on the log-scale, regardless of the initial value of net head acceleration. We will use linear mixed models to describe the longitudinal changes in log(net head acceleration) over the volume loads of exercise performed at each of the four study time points, and to test the significance of this change across the three exercise groups.

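### Section 9.1 claims a dose-response, but the randomised contrast is neck exercise versus none and the volume-load model has no test separating a graded from an all-or-none effect

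*Combined protocol and SAP*

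**What the plan says.** Section 9.1 states both confirmatory hypotheses as dose-response: for the primary endpoint a "dose-response effect for neck strengthening exercise on net head acceleration under direct load application proportional to the volume load of exercise", and for the secondary a "dose-response effect for neck strengthening exercise on net head acceleration under indirect load application proportional to the volume load of exercise".

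The randomised design has two levels. Section 6.2 gives "equal allocation to the control and high-intensity neck strengthening groups". Section 4.3 says of controls that "their exercise volume load will remain zero throughout the study". The summary of changes records "Low-Volume exercise group removed from protocol"; the sections it lists for that change include 9.2 but neither 9.1 nor 9.4.2.

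In the trained arm, load is measured. Under section 4.3, "the total cumulative exercise volume load will be defined as the sum of the individual session volume loads over all exercise sessions". Section 6.3 counts the programme as completed when "at least 20 of the 24 exercise sessions are attended", with a limit on missed sessions per four-week block.

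Section 9.4.2 plans "linear mixed models to describe the longitudinal changes in log(net head acceleration) over the volume loads of exercise performed" at the four time points, and a test of that change across exercise groups, of which it still counts three. It names no linearity test, no step or plateau alternative, and no dose test within the trained arm.

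The objective and endpoint in section 3 concern the effect of exercise at Assessment Time Point 4 and do not mention dose. Section 9.2 powers a comparison of slopes over time between control and high intensity.

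**The concern.** A dose-response proportional to load says more than that neck exercise works. It says that athletes who do more gain more, in proportion. The randomised comparison addresses only exercise against none. If training produced the same fixed reduction in every trained athlete by Assessment 2, whatever load was performed, a straight line over load would still slope downwards, because controls sit at zero and trained athletes do not. Read against section 9.1, that slope would count as support for a graded response.

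Such a shape is not far-fetched on the protocol's own account: section 2.2 reports non-linearity between neck strength and head acceleration and a possible ceiling effect. At stake is what a positive primary result may claim, in a project whose long-term goal is to optimise neck-strengthening programmes.

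**Working it through.** **1. The plan's power figure.** Inputs from sections 9.2 and 9.4.1: 30 per arm, d = .6 to 1.0 on the log scale, slope multiplier 1.25, alpha .05. Sidedness is not stated; two-sided reproduces the figure.

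Power = Φ(1.25·d·√(30/2) − 1.96), with √15 = 3.873.

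- d = .6: Φ(.75 × 3.873 − 1.96) = Φ(.945) = .83.
- d = 1.0: Φ(1.25 × 3.873 − 1.96) = Φ(2.88) = .998.

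The stated .83 and 1.0 reproduce as a two-arm comparison of slopes. No dose-response test enters the calculation.

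**2. What the load slope can conclude.** Trials were simulated with 30 per arm, four assessments, a random intercept and total SD 1, with 1,000 trials per scenario. The all-or-none truth is a constant drop of d from Assessment 2 onward in every trained athlete, regardless of load. The linear truth is a drop proportional to cumulative load. The documents do not give the correlation between visits or the between-athlete coefficient of variation (CV) of load, so they were assumed at .3 to .7 and 10% to 40%. Share of trials significant at d = .6:

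| Term tested | All-or-none truth | Linear truth |
|---|---|---|
| Load slope alone | 92% to 99% | 93% to 99.9% |
| Load slope with visit terms | 78% to 93% | 77% to 96% |
| Load slope with arm-by-visit terms | 4% to 6% | 5% to 45% |

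At d = 1.0 the first two rows are at least 99% under either truth; the third is about 5% under all-or-none and 10% to 84% under linear. A further run (visit correlation .3 or .6, load CV 15% to 40%) gave 75% to 100% with visit terms and 90% to 100% without, over d = .6 to 1.0 under the all-or-none truth. The planned slope therefore rejects about as often under one truth as under the other.

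**3. A model that can tell them apart.** One arm-by-post-baseline step term was placed beside volume load, with visit terms (visit correlation .3 or .6, load CV 15% or 40%). The load term was then significant in about 3% to 6% of trials under the all-or-none truth and about 28% to 98% under the linear truth, over d = .6 to 1.0. The arm-by-visit version under the same kind of assumptions has about 9% to 37% power at d = .6.

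**4. Power if the contrast is Time Point 4 instead.** With 30 per arm and d = .6:

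- Unadjusted: Φ(.6 × 3.873 − 1.96) = Φ(.364) = .64.
- Baseline-adjusted, r = .3: d/√(1 − r²) = .6/√.91 = .629; Φ(.629 × 3.873 − 1.96) = .68.
- Baseline-adjusted, r = .6: .6/.8 = .75, giving .83.

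The baseline correlation r is also an assumption.

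**The case against.** The strongest reply is that the design does contain several doses. Load is continuous, recorded at each session and accumulated, so each trained athlete contributes zero at baseline and three rising values at Assessments 2 to 4, alongside a concurrent zero-load control for time and growth. A reader might infer from the two arms that load falls into two clusters and that the data could never separate graded from all-or-none. The documents do not support that, and the step-term model shows that some separation is possible.

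Nor is the dropped arm the whole cause. With a hypothetical half-dose third arm, the load slope was still significant in 72% to 86% of trials at d = .6 under an all-or-none effect. What is missing is chiefly a test of shape.

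It is also fair to say that the exercise effect is already covered: section 3 asks for it, section 9.2 powers it, and section 9.4.2 compares groups. That a positive result would be reported as more volume giving more protection is a risk created by the wording, not something the plan states.

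The reply does not rescue the 9.1 claim. The variation within the trained arm is not randomised. Accumulation follows training time. Differences between athletes reflect attendance and strength: under section 6.1.2, shrugs use the most each athlete can comfortably handle, and section 2.2 links greater neck strength to lower head acceleration. The planned model does not isolate any of this.

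**Conclusion.** The concern stands in this limited form: under the 9.4.2 model, a significant volume-load slope supports an effect of neck exercise but does not support the proportional dose-response claimed in 9.1. Under an all-or-none effect at d = .6 to 1.0 the slope is significant in about 75% to 100% of simulated trials. The exact figures depend on the assumed visit correlation and spread of load, but the conclusion holds throughout the ranges tried.

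A reader might go further and infer that the primary test is invalid or its type I error inflated. That does not follow: the simulated trials contain a real exercise effect, so rejecting no effect is correct. Randomisation, the endpoint and the .83 power for the two-arm slope comparison are untouched. The 9.1 wording and the count of three groups look like leftovers from the three-arm design.

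**What to change.** - **Section 9.1.** Reword both hypotheses as superiority of high-intensity neck exercise over control, on the contrast section 9.2 already powers: the difference between arms in the slope of log(net head acceleration) over time. Sample size and power do not change.
- **Section 9.4.2.** State two exercise groups and name that contrast as the test.
- **If a Time Point 4 contrast is preferred**, to match the endpoint in section 3, adjust for baseline and restate power. At d = .6 with 30 per arm it is about .64 unadjusted and .68 to .83 adjusted for r = .3 to .6, against .83 now.
- **Dose-response.** Keep it as exploratory and label it non-randomised. Base any statement on a volume-load term beside an arm-by-post-baseline step term. Part of that term's information is growth of the arm difference across visits, which training time alone could also produce, so report the arm-by-visit version as a stricter check with lower power.

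The editing cost is two sentences in 9.1, a corrected group count and named contrast in 9.4.2, and one exploratory model with its check. The real cost is that dose-response ceases to be a confirmatory claim. The changes should be made before the analysis.

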#### **Secondary Efficacy Endpoint:**

There will be evidence of a dose-response effect for neck strengthening exercise on net head acceleration under indirect load application proportional to the volume load of exercise.

## 9.2 SAMPLE SIZE DETERMINATION

Our power calculation is based on AIM 1. Assuming net head acceleration (on the logarithmic scale) will follow linear trends over time, then our power calculation is based on comparison of the slope of this change, which has 9/14 of the variance, i.e., 36% less variance, than the underlying log(net head acceleration) measurements. As a result, the standardized effect size (Cohen's d value) of the slope is approximately 1.25 times greater than that of the underlying log(net head acceleration) measurements. Based on our own pilot data, we expect observed standardized effect sizes to be between .6 and 1.0 for log(net head acceleration), depending on the variability of the individual measurements across the 4 directions of motion. These values correspond with a 20% overall reduction in un-transformed net head acceleration. A total of 30 subjects in each exercise group (control and high intensity), will provide power of between .83 [for standardized effect size for log (net head acceleration) of .6 and 1.0 [for standardized effect size in the population. To account for the possibility of a drop-out rate of up to 20%, we will plan to enroll up to a total of 72 subjects.

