Objectives:		Primary Objective (AIM 1): To determine the effect of manual resistance neck strengthening exercise on net head acceleration during simulated sport-associated impacts to the head (direct loading condition). Secondary Objective (AIM 1): To determine the effect of manual resistance neck strengthening exercise on net head acceleration during simulated sport-associated impacts to the body (indirect loading condition). Exploratory Objective (AIM 1): To determine the effect of manual resistance neck strengthening exercise over time on neck strength, cervical muscle volume, neuromuscular recruitment, and net head acceleration under direct and indirect loading as well as during voluntary soccer heading. Exploratory Objective (AIM 2): To determine the relative influences of baseline neck strength and cervical muscle volume on net head acceleration during simulated sport-associated impacts to the head and body with and without volitional, anticipatory cervical muscle pre- contraction to brace for the impact.

Endpoints:	Primary Endpoint: Mean area under the net head acceleration vs. time curve during direct loading, with anticipatory bracing, at Assessment Time Point 4.
	Secondary Endpoint: Mean area under the net head acceleration vs. time curve during indirect loading, with anticipatory bracing, at Assessment Time Point 4.
Study Population:	Up to 72 male and female high school soccer athletes in and around Ann Arbor Michigan.
Phase:	N/A
Description of	University of Michigan.
Sites/Facilities Enrolling	
Participants:	
Description of Study	Neck strengthening resistance exercise.
Intervention:	
Study Duration:	Approximately 60 months.
Participant Duration:	Approximately 4 months.

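### The declared endpoint, 9.1, 9.2 and 9.4.2 do not share one primary contrast, so the stated power of .83 does not belong to the test in 9.4.2; separately, 72 enrolled covers 16.7% drop-out, not 20% (small effect)

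*Combined protocol and SAP*

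**What the plan says.** The synopsis (Section 1.1) declares "Primary Endpoint: Mean area under the net head acceleration vs. time curve during direct loading, with anticipatory bracing, at Assessment Time Point 4", and the table in Section 3 repeats it. Section 9.1 instead states a dose-response hypothesis, with an effect on "net head acceleration under direct load application proportional to the volume load of exercise".

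Section 9.2 bases power on a third quantity, the slope over time: "Assuming net head acceleration (on the logarithmic scale) will follow linear trends over time", the comparison is of slopes, a quantity "which has 9/14 of the variance, i.e., 36% less variance, than the underlying log(net head acceleration) measurements". Effect sizes of .6 to 1.0 on the log scale are expected from pilot data: "These values correspond with a 20% overall reduction in un-transformed net head acceleration". Then: "A total of 30 subjects in each exercise group (control and high intensity), will provide power of between .83" at the low end, rising to 1.0 at the high end. Enrolment follows from a "drop-out rate of up to 20%, we will plan to enroll up to a total of 72 subjects".

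Section 9.4.2 models "longitudinal changes in log(net head acceleration) over the volume loads of exercise performed at each of the four study time points" and tests that change across three exercise groups. Sections 4.1 and 6.2 describe two groups, control and high intensity. Section 4.3 says that the control group's volume load is zero for the whole study. Section 7.2 says that drop-outs are not replaced, and Section 9.3 keeps participants with partial data in the analysis.

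**The concern.** A power statement is informative only for the test it was computed for. Here power is computed for slope over time in two groups, the analysis section tests change over volume load in three groups, and the endpoint is a single visit. These are different regressors, different numbers of groups and different tested coefficients. If the text stays as it is, the primary test has to be settled later, and Section 6.2 says that the study statistician is not blinded to allocation.

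Two further points in 9.2 bear on the stated power. The drop-out allowance does not match the enrolment figure. The variance factor behind .83 also depends on how baseline is handled and on the within-athlete correlation, and neither is given.

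**Working it through.** **1. The stated power reproduces.** Inputs: 30 per group, d = .6, multiplier 1.25 (all 9.2); alpha .05 (9.4.1, sidedness not stated, two-sided assumed).
- Slope effect: .6 × 1.25 = .75. The exact multiplier is sqrt(14/9) = 1.247.
- Normal approximation: .75 × sqrt(30/2) = 2.905; 2.905 − 1.960 = .945; power .828. The t-test gives .815.
- At d = 1.0 (slope effect 1.25): .998 normal, .997 t. Both ends match the plan. A one-sided test would give .896 or .890 at d = .6, which does not match.

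**2. The contrasts side by side.**

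| Place | Quantity tested | Groups |
|---|---|---|
| 1.1 and 3 | value at Time Point 4 | not stated |
| 9.1 | change over volume load | not stated |
| 9.2 | slope over time | two |
| 9.4.2 | change over volume load | three |

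- Time Point 4 and slope over time can be the same contrast. With a linear trend, a common baseline and visits coded 0, 1, 2, 3, the Time Point 4 group difference is three times the slope difference. The plan does not say this.
- Volume load is a different regressor. With control volume load fixed at zero, the control group has no spread on that axis, so a control slope, and hence a difference in group-specific slopes, cannot be estimated. A single dose-response slope pooled over both groups, with controls as the zero-dose reference, can be. The plan gives neither the spread of volume load nor an effect per unit, so power for that model cannot be computed from the documents.
- For scale, an unadjusted Time Point 4 comparison: .6 × sqrt(15) = 2.324; 2.324 − 1.960 = .364; power .642 normal, .628 t.

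**3. Drop-out.**
- 60 × 1.2 = 72, but 72 × .8 = 57.6 (28.8 per group). The allowance that leaves 60 is 12/72 = 16.7%. Sixty completers at 20% loss would need 60/.8 = 75.
- Power at d = .6 with 28.8 per group: .812 normal, .799 t, against .828 and .815.
- Partial data, using the plan's 9/14 weighting. Slope information per group, in units of 1/visit variance, is 30 × 14 = 420 for the plan. With 36 per group and 20% leaving:
  - after visit 1: 36 × .8 × 14 = 403.2, power .812
  - after visit 2: 36 × (.8 × 14 + .2 × 1) = 410.4, power .819
  - after visit 3: 36 × (.8 × 14 + .2 × 5) = 439.2, power .844 (all normal)

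**4. Where 9/14 comes from.** 9/14 = 3²/(0² + 1² + 2² + 3²). Write rho for the within-athlete correlation, taken as equal between all visits (an assumption). The factor arises in several ways:
- a line through a fixed baseline with independent visits;
- a common baseline mean, where the factor is 9(1 − rho)/(14 − 36rho/(1 + 3rho)). This equals 9/14 at rho = 0, and again when 1 + 3rho = 36/14, that is rho = .524;
- an intercept per athlete, where the factor is 1.8(1 − rho), equal to 9/14 at rho = .643.

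Power at d = .6, 30 per group, normal approximation, with d taken on the total SD (an assumption):

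| Model | rho 0 | rho .5 | rho .6 | rho .8 |
|---|---|---|---|---|
| Linear time, common baseline | .826 | .815 | .867 | .983 |
| Linear time, intercept per athlete | .410 | .688 | .782 | .972 |
| Time Point 4 adjusted for baseline, factor 1 − rho² | .642 | .765 | .828 | .972 |

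The common-baseline row has its minimum, .759, near rho .25. At d = 1.0 that model gives .99 or more throughout. The intercept-per-athlete model gives .823 at d = 1.0 and rho 0. These values show sensitivity only; the documents give no rho.

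**The case against.** The best defence is that a mixed model covers all of this. Under the linear trend assumed in 9.2, with baseline means equal in expectation by randomisation, slope and Time Point 4 are one contrast, and 9.4.2 can be read as a pooled dose-response model that agrees with 9.1. Both halves stand as far as they go. They still leave two tests, one over time and one over volume load, and power is given only for the first.

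Four stronger readings are tempting, and the documents do not support them:
- *The analysis in 9.4.2 cannot be fitted.* This is true only of a comparison of group-specific slopes over volume load.
- *The .83 is an arithmetic error, or needs independent visits.* It reproduces, and the same factor arises at rho of about .52 or .64. What is missing is the reporting of rho and of the SD behind d.
- *Enrolment must rise to 75.* The cost of the wrong allowance is .016 in power at d = .6, partial data are kept, and late drop-out would more than offset it.
- *The background correlations fix rho.* Section 2.2 reports r of .60 to .76 between neck circumference and head acceleration, with squares of .36 to .58. If that component is stable over 12 weeks and residuals are not negatively correlated, these are lower bounds on rho, not a span. They also come from both bracing conditions, while the endpoint is braced loading only.

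**Conclusion.** Two statements are wrong as written. The main one is that the sections do not share a primary contrast and 9.4.2 counts a group that no longer exists, so .83 cannot be read as the power of the test in 9.4.2. How far the power of the intended test differs from .83 cannot be settled from the documents; the .64 for an unadjusted Time Point 4 comparison shows that the choice matters at d = .6. The smaller one is the drop-out allowance, worth at most about one and a half power points at d = .6 under the plan's own weighting.

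The missing rho and SD are a reporting gap, not an error. Power at d = .6 could lie above or below .83. At d = 1.0 the conclusion is safe under a common baseline and a linear trend. A reader might infer that the trial is underpowered; the documents do not show that. The figures rest on two-sided .05, equal correlation between visits and d standardised on the total SD. If d was standardised on a change-score or residual SD, the rho table does not apply.

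**What to change.** No change in enrolment.

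(a) In 9.2, state that 72 covers 16.7% drop-out, or keep 20% and give power of about .81 (normal) or .80 (t) at d = .6, before partial data are counted.

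(b) In 9.4.2, change three groups to two. The sponsor should name one primary contrast and use it in the endpoint, 9.1, 9.2 and 9.4.2. It can be the two-group difference from a mixed model over time, stating whether time is linear and how baseline is handled, or a pooled volume-load model with controls at zero. The other becomes supporting. Align the secondary hypothesis in 9.1, the sex analysis in 9.4.6 and the soccer-heading analysis in 9.4.8, which depend on the same choice.

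(c) In 9.2, give power for the named contrast at d = .6 and d = 1.0, with the SD on which d is standardised and a rho range from the pilot data.

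The cost is text edits in those sections and a stated power that may be less favourable at d = .6. If the time contrast is chosen, the dose-response hypothesis moves from primary to supporting, which is a change of substance and should be recorded as such. If time is modelled as linear, the Time Point 4 estimate depends on that trend holding.
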